4.2 PARTICIPANTS

We will aim to recruit 42 adults who meet NIAAA criteria for at-risk drinking; >7/14 standard drinks per week for women/men, with at least one past-month heavy drinking episode defined as 4/5+ standard drinks for women/men. To ensure a range of alcohol use in the sample we will aim to recruit an even number of participants from AUDIT zones 1, 2 and 3 (AUDIT total score = 0-7, 8-15, and 16-19 respectively) which reflect different levels of alcohol use health risk severity [57]. The AUDIT is a validated screening tool that indexes alcohol use severity, but is not a diagnostic instrument. Typically an AUDIT score of 20 or greater indexes elevated risk for alcohol use disorder; those with scores of 20+ will be excluded. In addition, we will aim to recruit an even distribution of males and females across AUDIT zones. Participants will be recruited via flyers and social media ads from the triangle area (Chapel Hill, Raleigh, Durham). Interested participants will fill out an online pre-screen survey using Research Electronic Data Capture (REDCap) to determine initial eligibility. We estimate screening 250 people will yield 55 eligible participants to consent. Accounting for study drop-outs, we expect that 55 consents will allow for a final sample size of 42 who complete all study procedures, which is a feasible goal for the 12-month study. Potentially eligible participants will be contacted via email to schedule a virtual visit including additional screening and informed consent. A research assistant will explain the study requirements and both parties will sign the consent documents via REDCap if agreeing to enroll in the study. The DSM-5 SCID will then be administered to screen for alcohol and substance use disorder.

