Participants will receive a beverage containing either a dietary supplement (10g Fibersol®-2 mixed with water and aspartame sweetener for taste + 725mg decaffeinated green tea extract capsule) or a calorically matched placebo supplement (Aspartame sweetener mixed with water + aspartame capsule) counterbalanced at two separate visits. Forty-five minutes after the dietary supplement, the second blood sample is taken. Next, a priming drink (calculated to achieve 30mg% BAC) is administered to stimulate craving for alcohol [66, 67]. Drinks will consist of 40 proof vodka and a sugar-free cranberry juice mixer at a 1:5 ratio. Doses are calculated to achieve target BACs based on sex and body weight using formulas established in prior research [68]. Fifteen minutes after the priming drink, a novel alcohol-specific satiety questionnaire will be administered followed by alcohol incentive motivation tasks (alcohol purchase task; APT [69], dot probe attentional bias to alcohol-related stimuli), additional validated alcohol subjective response questionnaires (Drug Effects Questionnaire; DEQ[70], Biphasic Alcohol Effects Scale; BAES [71], Alcohol Urge Questionnaire; AUQ [72], Subjective Effects of Alcohol Scale; SEAS [73]), *hunger, fullness, and satiety* visual analogue scale (VAS) items, a BACtrack S80 BrAC measure, and a fingerprick blood sample.

Alcohol-specific satiety paced drinking procedure

Then over a 2-hour period, 5 additional mini-drinks (calculated to achieve an estimated BAC increase of 10mg% each or placebo) are administered with 15 min absorption time between each drink to reach an estimated maximum BAC of 60-70mg%, reflecting a moderate level of alcohol exposure (80mg% is the conventional cutoff for “binge” exposure). Participants have 3 minutes to finish each drink (Average volume of a drink, alcohol+mixer at a 1:5 ratio is 8/5oz for a man/woman). This paradigm is designed to approximate a natural drinking pace, while controlling for the BAC during subjective satiety assessment. The control session will control for expectations of increased satiety with subsequent drinks. Control drinks contain cranberry juice with an alcohol mask (rim sprayed with vodka) matched in total volume to the alcohol drinks. Participants will be told that all drinks contain alcohol. Subjective response questionnaires are repeated 15 minutes after each drink. BACtrack S80 BrAC measures are repeated every 15 minutes.

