To analyze study aim 3, multi-level regression models will be used to assess within-person changes on repeated measures along with between-person individual differences. A linear growth curve model will be used to test the hypothesis that alcohol-specific satiety increases with time and additional drinks. Timepoint (1-6) and drug (alcohol or placebo) will be included in the model as within subject factors. Compared to placebo, alcohol is predicted to be associated with higher rates of change (slope) in satiety. Next, AUDIT will be included as a continuous predictor of slope in the model to test the hypothesis that participants with fewer alcohol dependence symptoms (lower AUDIT scores) report reduced satiety. Finally, subjective craving scores (Alcohol Urge Questionnaire; AUQ) from each timepoint will be included in the model. The effect of satiety over time is expected to remain significant after controlling for craving. Alcohol-specific satiety is expected to be negatively associated with measures of reward and incentive motivation for alcohol (BAES, APT, Dot Probe). Outcomes from each of these measures will be included in separate multi-level models with satiety scores as the primary dependent measure and timepoint (1-6) and drug (alcohol, placebo) as within-subject factors to determine the effect of additional dependent measures on within-person change in alcohol specific-satiety over time (slope).

To analyze aim 4, a repeated measures analysis of variance (ANOVA) will be used to assess the effect of a dietary supplement on alcohol-specific satiety in a 2(alcohol, placebo) x 2(timepoints) design. It is

predicted that compared to placebo, a GLP-1 stimulating dietary supplement will increase alcohol-specific satiety.

To analyze aim 5, linear regression will be used to assess the association between HMGB1 levels as a function of BrAC during the laboratory alcohol sessions. Data processing and analyses will be completed in R and SPSS.

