8.2 SAMPLE SIZE JUSTIFICATION

An a priori power analysis was conducted using G*Power version 3.1.9.7 (Faul et al., 2007) to determine the minimum sample size required to test the study aims. Results indicated the required sample size to achieve 86% power for detecting a medium effect, at a significance criterion of $\alpha = .05$, was $N = 42$ for within-between interactions on repeated measures.

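### Aim 3 tests AUDIT against the satiety slope without sex; prespecifying sex and sex × timepoint costs almost nothing and may recover a few points of power

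*Combined protocol and SAP*

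**What the plan says.** Section 8.1 builds the Aim 3 model in steps. Timepoint (1 to 6) and drug (alcohol or placebo) enter as within-subject factors. Next, "AUDIT will be included as a continuous predictor of slope in the model". Craving scores are added last. Neither sex nor sex × timepoint is named, and no AUDIT × drug term is named either, so as written the AUDIT test is AUDIT × timepoint.

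Three other places bear on sex:

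- Section 4.2 (Participants) plans to "recruit an even number of participants from AUDIT zones 1, 2 and 3", and adds that "we will aim to recruit an even distribution of males and females across AUDIT zones". It also states that "we expect that 55 consents will allow for a final sample size of 42".
- Section 4.3 (Study visit procedures) gives the average drink volume: "alcohol+mixer at a 1:5 ratio is 8/5oz for a man/woman". Control drinks have the same total volume as the alcohol drinks. The same section says "Doses are calculated to achieve target BACs based on sex and body weight", so sex is known for every participant who is dosed.
- Section 8.1 opens with exploratory tests of participant characteristics against outcomes, and section 4.3 collects baseline measures to look for moderators in secondary analyses. Neither adjusts the AUDIT test.

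**The concern.** The outcome is satiety, and the procedure gives men and women different volumes to drink. At 8 and 5 oz per drink, five paced drinks come to 5 × 8 = 40 oz for men and 5 × 5 = 25 oz for women, a ratio of 8/5 = 1.6, in both drink conditions. Any part of the satiety rating that follows fullness would then rise faster in men. That between-person difference would sit in the random-slope variance, against which AUDIT × timepoint is tested.

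Two things could follow. If sex is balanced across AUDIT, the AUDIT estimate is unaffected but the test is less precise than it could be. If balance is missed, part of a sex difference can appear as an AUDIT effect. Balance is an aim. The analysed set is the 42 who finish out of 55 who consent. Section 6.2 replaces non-completers without saying that replacements are matched on sex or AUDIT zone.

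**Working it through.** **The plan's own figure.** Section 8.2 reports "86% power for detecting a medium effect" at N = 42, "for within-between interactions on repeated measures". It does not state the number of groups k, the number of measurements m or their correlation. With the G*Power formula λ = f²·N·m/(1 − corr), df = (k − 1)(m − 1) and (N − k)(m − 1), and assumed values f = 0.25, corr = 0.5, k = 6, m = 5:

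- λ = 0.0625 × 42 × 5/0.5 = 26.25, df = 20 and 144, power = 0.859.

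So the figure can be reproduced, but other inputs also reach 86% (for example k = 2, m = 2, correlation 0.459). It does not show what was assumed about sex. It is also not a calculation for a continuous predictor of slope, so the effect of adding sex is worked out directly below.

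**Power for AUDIT on person-level slopes.** Inputs: N = 42 (8.2), two-sided α = 0.05, and sex uncorrelated with AUDIT (the balance aim is met). ρ, the correlation of sex with the slope, is assumed. A medium effect is read two ways: r = 0.30, so R² = 0.09, or f² = 0.15, so R² = 0.15/1.15 = 0.1304.

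- Without sex: f² = R²/(1 − R²), error df 40.
- With sex: f² = R²/(1 − R² − ρ²), error df 39.
- λ = 42·f² in both cases, referred to the noncentral F.

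Example for r = 0.30:

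- Without sex: f² = 0.09/0.91 = 0.0989, power 0.5116.
- With sex at ρ = 0.28: f² = 0.09/(1 − 0.09 − 0.0784) = 0.1082, power 0.5475.

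| ρ | Power, r = 0.30 | Gain (points) | Power, f² = 0.15 | Gain (points) |
|---|---|---|---|---|
| sex omitted | 0.5116 | – | 0.6877 | – |
| 0 | 0.5111 | −0.1 | 0.6872 | −0.1 |
| 0.14 | 0.5198 | 0.8 | 0.6970 | 0.9 |
| 0.28 | 0.5475 | 3.6 | 0.7278 | 4.0 |
| 0.35 | 0.5702 | 5.9 | 0.7520 | 6.4 |
| 0.50 | 0.6458 | 13.4 | 0.8263 | 13.9 |

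The break-even point is a sex share of slope variance of about 0.1%.

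**Which ρ could the volume difference produce?** Suppose the slope were fully proportional to volume, with coefficient of variation CV within each sex. Then d = (8 − 5)/(6.5·CV), where 6.5 is the mean of 8 and 5, and ρ = d/√(d² + 4).

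- CV 40%, 60%, 80%, 100%: ρ = 0.50, 0.36, 0.28, 0.22.

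If only half of the slope were volume-driven, d halves:

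- Same CVs: ρ = 0.28, 0.19, 0.14, 0.11, and the gain is 4 points or less throughout.

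Both the CVs and the share are assumptions.

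**If balance is missed.** I simulated a null AUDIT effect with 14 people per zone and AUDIT uniform within each zone, and tested AUDIT at a nominal 5%.

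| Men per zone (1/2/3) | Sex omitted, ρ = 0.2 / 0.35 / 0.5 | Sex included |
|---|---|---|
| 9/7/5 | about 5.5% / 7% / 8% | about 5% |
| 10/7/4 | about 7% / 10% / 15–16% | about 5% |

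With exact 7/7/7 balance and ρ = 0.5, the test without sex rejects about 3% of the time. It is then conservative, which is the same loss of precision seen from the other side.

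**The case against.** The strongest reply is that no loss has been shown. Nothing in the documents says that sex predicts the satiety slope, and if it does not, adjustment gains nothing. That stands, and it is why the size is given only as a range. A reader might infer from the drink volumes that power is certainly being lost. The documents do not support that, for three reasons:

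- The volume gap comes from dosing both sexes to common target BACs, so it is not a difference in intended alcohol exposure.
- The outcome is an alcohol-specific satiety questionnaire, and hunger, fullness and satiety are rated separately on visual analogue scales. That fullness drives the alcohol-specific score is conjecture.
- Because control drinks are matched in volume, an additive volume effect cancels in the alcohol-versus-placebo slope contrast. The argument reaches AUDIT × timepoint pooled over drug, which is the test as written, and not that contrast.

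A reader might also treat sex as a stratification factor that the model is obliged to carry. Section 4.2 sets a recruitment aim. Sex is not a stratum for randomisation, and leaving a recruitment target out of the model does not make the analysis invalid. Nor is AUDIT on slope named as the main test: the synopsis lists five aims for pilot data and ranks none of them.

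The plan does not ignore participant characteristics either. It includes exploratory tests, and section 4.1 mentions fat-free mass as a later covariate. But the exploratory tests leave the AUDIT test unadjusted, and 8.1 does not bring fat-free mass into Aim 3. The balance aim gives real protection against confounding, though no guarantee.

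**Conclusion.** The point holds as a minor, conditional one. The Aim 3 model omits sex although recruitment aims to balance it across AUDIT zones and the procedure gives the sexes different drink volumes. At N = 42 with a medium effect, the power forgone runs from nothing to about 4 points for sex–slope correlations up to 0.28. It is about 6 points at 0.35. It reaches 13 to 14 only at 0.5, where sex would explain 0.5² = 25% of slope variance. All of these correlations are assumed, and the calculation treats person-level slopes as the outcome with sex uncorrelated with AUDIT.

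If balance is achieved, the AUDIT estimate is not biased and only precision is at issue. If it is missed and sex does predict slope, the unadjusted test can exceed its nominal 5%, slightly for a 9/7/5 split and materially for 10/7/4 at the higher correlations.

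**What to change.** In section 8.1, Aim 3, prespecify sex and sex × timepoint in the model that tests AUDIT × timepoint. If AUDIT × drug × timepoint is also to be tested, add sex × drug × timepoint. The interaction with timepoint is the part that matters: a sex main effect alone shifts the level of satiety and leaves the slope variance where it was.

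The cost is one sentence, one or two degrees of freedom and no new data, with about 0.1 power point lost if sex is unrelated to slope. Settling it before the data are seen also avoids a post hoc choice of covariate.

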The dot probe is a measure of cognitive attentional bias used in prior studies thought to reflect the incentive salience of alcohol related stimuli [85, 86]. This task will be administered on E-Prime software. Subjects are sat at a computer and shown left-right pairs of images on a screen for 1000ms followed by a white dot in place of one of the images. Participants are instructed to respond to the dot probe target with a key using their left hand if the dot is on the left side, and the right hand if the target appears on the right side. Pairs of images include alcohol related images matched with control images (non-alcohol beverages such as soda, a glass of water, etc.). 10 image pairs are presented four times each for a total of 40 critical test trials. 40 additional trials are randomly interspersed with critical trials which feature neutral filler images (office supplies, etc.). The target may either be congruent to the alcohol-related stimuli (target appears on the same side as the alcohol-stimuli) or incongruent (target appears on the side of the control stimuli). The task takes 5 minutes to complete. Faster reaction times to alcohol-related imagery on congruent trials (alcohol image displayed on the same side as the dot probe target) and slower reaction times on incongruent trials reflect increased attentional bias towards the alcohol-related stimuli. Therefore, reaction time to alcohol cues > neutral cues on incongruent > congruent trials reflect the attentional bias score [86]. Attentional bias will be assessed before and after alcohol administration and change scores will be calculated.

List of Measures (See section 1.3 for assessment time points)

1. Demographics form
2. Alcohol Use Disorder Identification Test (AUDIT)
3. Inventory of Drinking Situations (IDS)
4. Obsessive Compulsive Drinking Scale (OCDS)
5. Reward-based Eating Drive Scale (RBEDS)
6. Body Perception Questionnaire (BPQ)
7. Drinking Motives Questionnaire (DMQ)
8. Comprehensive Relative Autonomy Index for Drinking (CRAI- D)
9. Alcohol Sensitivity Questionnaire (ASQ)
10. Impaired Control Scale (ICS)
11. Alcohol-specific satiety questionnaire
12. Drug Effects Questionnaire (DEQ)
13. Visual Analogue Scale items (VAS)
14. Biphasic Alcohol Effects Scale (BAES)
15. Subjective Effects of Alcohol Scale (SEAS)
16. Alcohol Urge Questionnaire (AUQ)

17. Alcohol Purchase Task (APT)
18. Dot Probe attentional bias to alcohol related cues task
19. Breath Alcohol Concentration (BrAC)

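### Aim 3 enters BAES and AUQ into the satiety models with no within/between-person split, so the BAES test can hide or mimic the within-person link it targets

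*Combined protocol and SAP*

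**What the plan says.** Section 8.1 describes the Aim 3 analyses in general terms: "multi-level regression models will be used to assess within-person changes on repeated measures along with between-person individual differences". The base model is a linear growth curve for satiety: "Timepoint (1-6) and drug (alcohol or placebo) will be included in the model as within subject factors". Two kinds of time-varying score are then added.

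- **Craving (AUQ).** "Finally, subjective craving scores (Alcohol Urge Questionnaire; AUQ) from each timepoint will be included in the model". The stated expectation concerns the satiety trajectory, not the craving coefficient: "The effect of satiety over time is expected to remain significant after controlling for craving".
- **Reward and incentive measures (BAES, APT, Dot Probe).** Satiety is expected to be negatively associated with these. "Outcomes from each of these measures will be included in separate multi-level models with satiety scores as the primary dependent measure", and the purpose is "to determine the effect of additional dependent measures on within-person change in alcohol specific-satiety over time (slope").

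Section 4.3 lists AUQ and BAES among the subjective response questionnaires and says "Subjective response questionnaires are repeated 15 minutes after each drink". It lists APT and Dot Probe as tasks and does not clearly repeat them after each drink. For Dot Probe it adds: "Attentional bias will be assessed before and after alcohol administration and change scores will be calculated".

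No section mentions person-mean centring, a person-mean term, or any other way to split a repeatedly measured covariate.

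**The concern.** BAES is rated alongside satiety at every timepoint in both sessions, and the plan wants to know whether it goes with change in satiety inside a person. An unsplit score also carries stable differences between people, such as trait level and general rating style. In a random-intercept model its single coefficient is a weighted average of the within-person association and the between-person association. The second can be of a different size, or of opposite sign.

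If people who rate high on one scale tend to rate high on the other, a true negative within-person link is pulled towards zero. If the between-person link is negative, the model can show support when no within-person link exists. Either way, the result would be reported as an effect on within-person change.

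**Working it through.** **Inputs from the plan.** 6 timepoints x 2 drug conditions gives T = 12 ratings per person (8.1). N = 42 and alpha = .05 (8.2; two-sided assumed).

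**Assumed, because the documents give no values.** Random intercept only; scores entered as measured; total variance 1 for each scale; ICC 0.7 for the score and 0.6 for satiety; within-person correlation -0.15; between-person correlation r varied.

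The plan's own 86% power is for a within-between interaction. It states no number of groups, number of measurements or correlation, so it cannot be uniquely reproduced. It does not cover this test, and nothing below depends on it.

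**Step 1. Weight on the between-person slope.**
b = (1 - w) x within slope + w x between slope, with w = psi B / (psi B + W), psi = se² / (se² + T su²), B = T x ICC + (1 - ICC), W = (T - 1)(1 - ICC). ICC here is that of the score; se² and su² are the residual and intercept variances of satiety.
With satiety ICC 0.5, psi = 1/13 = 0.077:
- score ICC 0.5: B = 6.5, W = 5.5, w = 0.500/6.000 = 8%
- score ICC 0.7: B = 8.7, W = 3.3, w = 0.669/3.969 = 17%
- score ICC 0.9: B = 10.9, W = 1.1, w = 0.838/1.938 = 43%

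**Step 2. Worked case, ICCs 0.7 and 0.6, r = +0.4.**
- Within slope = -0.15 x √0.4/√0.3 = -0.173.
- Slope on observed person means = (0.4 x √(0.7 x 0.6) - 0.173 x 0.3/12) / (0.7 + 0.3/12) = (0.259 - 0.004)/0.725 = 0.352.
- se² = 0.4 x (1 - 0.15²) = 0.391. Intercept variance around the fitted slope: su² = 0.6 + 0.7b² - 2b x 0.259 = 0.670 at the solution b = -0.116.
- psi = 0.391/(0.391 + 12 x 0.670) = 0.0464; psi B = 0.404; w = 0.404/3.704 = 0.109.
- b = 0.891 x (-0.173) + 0.109 x 0.352 = -0.116, about a third short of -0.173.
- SE unsplit = √(0.391/(42 x 3.704)) = 0.0501, so z = 2.31 and power is 64%. SE split = √(0.391/(42 x 3.3)) = 0.0531, so z = 3.26 and power is 90%.

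The same formulas for other r, beside simulated random-intercept fits (rate of a significant negative coefficient):

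| Within corr. | r | Unsplit b | Unsplit: formula / simulated | Split: formula / simulated |
|---|---|---|---|---|
| -0.15 | +0.4 | -0.116 | 64% / 65% | 90% / 90% |
| -0.15 | 0 | -0.154 | 87% / 86% | 90% / 89% |
| -0.15 | -0.4 | -0.199 | 98% / 98% | 90% / 92% |
| 0 | -0.4 | -0.045 | 14% / 15% | 2.5% / 2% |

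The split test does not depend on r, so the 89% to 92% spread is simulation noise.

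**Step 3. Effect on slope.** Write the score as person mean + deviation. Then score x time = (person mean x time) + (deviation x time). The first term captures whether people with a higher average BAES have a different satiety slope, which is a between-person question. One coefficient for the product forces both terms to share a value, so the blend carries over.

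**Step 4. AUQ as an adjustment covariate.** The quantity tested is the adjusted satiety slope. This was simulated for the time-by-drug term (500 trials; satiety residual and intercept SD 1, score variance 1).
- Craving has no trend by drug, true slope 0.30: 0.297 unsplit, 0.298 split.
- Craving rises 0.5 SD under alcohol, within slope -0.2, between slope +0.8, true slope 0.50: 0.47 / 0.44 / 0.32 unsplit at score ICC 0.5 / 0.7 / 0.9, against 0.50 split.
- Same rise, true slope 0, within +0.4, between -0.5: rejection 5% / 5% / 10% unsplit, against about 4% split.

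**The case against.** **Not splitting can be the better choice.** If the two associations are equal, the unsplit score is unbiased and uses more information. If both are negative it is more powerful, as the r = -0.4 row shows. This stands: the split is not free. But the plan neither assumes nor tests equality, and the extra power at r = -0.4 has the same source as the 15% false support when no within-person link exists.

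**The plan never says the scores enter uncentred.** True; that is inferred from silence. It is the plain reading, and it is what software does unless told otherwise.

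**AUQ has no coefficient hypothesis.** A reader might infer that the power and false-support figures apply to craving. The documents do not support that: the negative-association sentence names BAES, APT and Dot Probe, and craving is there only to be controlled for. Step 4 is the relevant check for AUQ.

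**Not every reward measure is affected.** A reader might also infer that all reward scores enter at each timepoint. Dot Probe is a before/after change score, and APT is not clearly repeated per drink. Of the three, only BAES clearly fits.

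**The stakes are modest.** Section 3 lists these as secondary measures for Aim 3, and the synopsis calls the study a pilot. That limits the priority of the point but does not answer it.

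**Conclusion.** The concern holds for BAES and, in a weaker form, for AUQ. For BAES the plan states a within-person target and gives no rule that isolates it. The size depends on assumed ICCs and on within- and between-person associations that differ: from 25 points of power lost (90 - 65) at r = +0.4, through about 3 points (89 - 86) at r = 0, to a gain at r = -0.4, with false support of about 15% against 2% in the null case. These figures are for a main-effect coefficient under a random intercept only. The documents do not state the random-effects structure, and the score-by-time version is argued from the algebra, not sized here.

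For AUQ the adjusted slope changes little unless craving itself trends by time or drug. It would go too far to conclude that Aim 3 as a whole is compromised: the unadjusted growth model and the AUDIT test contain no such covariate and are unaffected. This should be settled before analysis, but it does not threaten the main Aim 3 result.

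**What to change.** In section 8.1, state that each covariate rated at every timepoint (BAES and AUQ) enters as the participant's mean plus the deviation of each rating from it. A session mean may be added to separate session-to-session from moment-to-moment differences, since a mean over both sessions leaves these mixed in the deviation. Where the effect on slope is the target, give each term its own interaction with time. Test the within-person hypothesis on the deviation terms, and report the person-mean terms as between-person associations.

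Do not apply this to Dot Probe. Apply it to APT only if it is repeated at each timepoint, and say at which timepoints it enters.

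Cost: a sentence or two in the plan, one or two extra parameters per model, no new data, and some loss of power if the two associations agree in sign.

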naturalistic drinking contexts to assess the strength of the association between a novel TAC sensor (BACtrack Skyn) and breath alcohol (BrAC) measurements. In addition, we will also use a small non-intrusive light-based blood flow measurement device (placed on the participant's finger) and validate these measurements against the other metrics. These aims will be accomplished using data from two half-day visits to our lab at UNC campus, 1-2 days apart, followed by a 7-day remote assessment study and a final brief discharge visit (Figure 1). Lab visits involve a novel self-report questionnaire to assess alcohol-specific satiety during a paced alcohol challenge paradigm. In addition, on each of the two sessions in counterbalanced order, participants receive either a dietary supplement intended to stimulate postprandial GLP-1, or a calorically matched placebo to assess the effect of GLP-1 stimulation on alcohol-specific satiety. Two blood samples will be collected at each session to confirm plasma levels of glucagon-like peptide 1 (GLP-1). Blood fingerprick samples will be used to measure high-mobility group box 1 (HMGB1) inflammatory marker at three timepoints after alcohol administration. Additional measures of reward and incentive motivation for alcohol will be included to test the hypothesis that satiety is associated with reduced incentive motivation for alcohol reward. At the end of the second lab visit participants will be oriented to the 7-day remote assessment study. During the 7-day remote visit participants will be asked to wear the Skyn sensor continuously across 24-hours/day, except when bathing/showering or charging the device, and to initiate EMAs if they start an alcohol drinking bout. During drinking bouts, and for up to one hour following drinking bouts, participants will be prompted to record their BrAC every 20 minutes and to self-report the number of drinks consumed since the prior survey and subjective intoxication. Each morning, participants will complete daily diaries reporting alcohol-related harms experienced on the prior day. Following the 7-day remote visit, participants will complete a final discharge visit to return study devices, complete a timeline follow-back, and undergo a dual x-ray absorptiometry (DEXA) scan to assess fat-free mass, which will be included as a covariate in subsequent analyses to account for alcohol-elimination rate [56]..

[figure not shown]

Figure 1. Diagram of lab session procedures

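### The Aim 3 hypothesis is an association between satiety and reward or incentive motivation, but the models are aimed at the satiety slope, which does not test it

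*Combined protocol and SAP*

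**What the plan says.** Section 8.1 (Aim 3) states the hypothesis as an association: "Alcohol-specific satiety is expected to be negatively associated with measures of reward and incentive motivation for alcohol (BAES, APT, Dot Probe". Section 4.1 says the extra measures are there "to test the hypothesis that satiety is associated with reduced incentive motivation for alcohol reward". Neither sentence mentions change over time.

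On the analysis, Section 8.1 says: "Outcomes from each of these measures will be included in separate multi-level models with satiety scores as the primary dependent measure". Timepoint (1–6) and drug are the within-subject factors, and the stated purpose is "to determine the effect of additional dependent measures on within-person change in alcohol specific-satiety over time (slope".

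Two other predictors in the same paragraph are worded differently from each other. For AUDIT, "AUDIT will be included as a continuous predictor of slope in the model". For craving, "subjective craving scores (Alcohol Urge Questionnaire; AUQ) from each timepoint will be included in the model", followed by a statement about controlling for craving. The paragraph also uses slope to mean the rate of change in satiety.

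Section 4.3 repeats the subjective response questionnaires, BAES among them, 15 minutes after each drink. It lists APT and dot probe separately as incentive motivation tasks and does not say that they repeat after each drink. It defines attentional bias as a change score from before to after alcohol. Section 3 lists stimulation, sedation, demand and attentional bias as secondary measures for Aim 3.

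**The concern.** An association and an effect on slope are different parameters with different null hypotheses. The null for the hypothesis is that satiety and the measure are unrelated. The null for an effect on slope is that the measure does not alter how fast satiety changes, which for a measure rated at every timepoint means that the association is the same throughout the session. A strong, steady negative association satisfies the second null.

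The satiety questionnaire is new, and this is the plan's stated test of whether satiety goes with lower motivation for alcohol. If the slope term is taken as that test, a null result could be reported as no relation when the predicted relation is present. A significant result could be reported as support when there is no relation on average.

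Section 8.1 also leaves open which coefficient decides the question, whether a main effect is kept beside an interaction, how timepoint is coded, and whether within-person and between-person association are separated.

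**Working it through.** **The plan's own power figure.** Section 8.2 gives 86% power at N = 42, alpha .05, for a medium effect in a within-between interaction. With f = 0.25, correlation 0.5, 6 groups and 5 measurements (none of these values is stated in the plan), the noncentrality is f²·N·m/(1 − ρ) = 0.0625 × 42 × 5 / 0.5 = 26.25. The degrees of freedom are 5 × 4 = 20 and 36 × 4 = 144, and power is 0.859. The figure can be reproduced, but it concerns a different test and says nothing about the satiety–motivation association.

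**The algebra.** Write satiety for person i at timepoint t as

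S = aᵢ + b·t + β·x + γ·x·t + error,

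where x is the measure. The slope of satiety on time is b + γ·x, so an effect of x on slope is γ. A constant association means β < 0 and γ = 0. With the main effect in the model, the null for γ is then true whatever β is, and rejection occurs at alpha.

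The reverse case: let γ = -0.1 per timepoint with time centred at 3.5 and β = 0. The associations at timepoints 1 to 6 are +0.25, +0.15, +0.05, -0.05, -0.15 and -0.25, which sum to zero. The slope effect is real and the average association is nil.

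A third reading is that effect on slope means how far the time coefficient moves once x is added. If x has trend d per timepoint, the movement is β·d. A measure with no trend (d = 0) leaves the slope unchanged however strong the association, so this reading misses the hypothesis too.

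**Inputs for the simulations.** From the documents: 42 completers (Section 4.2), and two drug conditions by six timepoints (Section 8.1). Assumed, because the documents give no values:
- Scenario A: residual SD 1, random person intercepts and slopes, session effects, measure autocorrelation 0.5. Analysis: within-person regression with person-clustered standard errors, 2,000 runs.
- Scenario B: measure SD 1 with half its variance between persons; satiety variances 0.5 (person), 0.1 (session), 0.01 (slope) and 0.5 (residual). Analysis: generalised least squares with the true covariance, 1,000–5,000 runs.

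**Measure taken at each timepoint, constant association β (SD per SD), two-sided .05**

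| β | Association term, A | Association term, B | Measure × timepoint, A |
|---|---|---|---|
| 0 | 6.5% | – | 5.8% |
| -0.10 | – | 58% | – |
| -0.15 | 71.6% | 89–90% | 5.7% |
| -0.20 | 91.2% | 99% | 5.7% |
| -0.30 | 99.8% | – | 6.3% |

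In scenario A the interaction rejects as often with a strong association as with none. In scenario B at β = -0.20 (5,000 runs each) it rejects 5.2%, 4.6% and 4.8% of the time for measures varying by timepoint, session and person. Simulation error there is about 1.96 × √(0.05 × 0.95/5000) = 0.6 points, so these values are alpha.

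**Association term when the measure varies less often (scenario B)**

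| β | Session-level | Person-level |
|---|---|---|
| -0.10 | about 25% | about 12% |
| -0.15 | about 46% | about 24% |
| -0.20 | 72% | 40% |
| -0.30 | 96% | about 68% |

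**Zero average association, slope effect -0.1 per timepoint (scenario A).** The slope term rejects 83.0% of the time and the association term 5.9%.

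**What the unstated choices do** (scenario B assumptions, β = -0.20, measure at each timepoint; the third figure is from fitted mixed models without session variance, 100 runs):
- interaction, main effect present: about 5%
- main effect beside the interaction, time centred: 99%; time zero at the first timepoint: about 82%
- interaction without the main effect, time coded 1–6: about 96%

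**Raw measure against person-mean split** (mixed model, 200 runs, no within-person association). With a between-person correlation of -0.5 or +0.5, the raw main effect rejects 14.5% or 18.5% of the time. The deviation from the person's own mean rejects 6% in both cases. Simulation error on the raw figures is about ±5 points.

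**The case against.** The strongest reply is that Section 8.1 says the measures are included in the models and does not say that only an interaction will be tested. Their inclusion wording resembles that for craving, which is a covariate, more than that for AUDIT, which is explicitly a slope predictor. A standard model with the interaction also estimates the main effect, and with time centred that main effect keeps its power. This stands: the plan does not commit to ignoring the main effect. It does not dispose of the point, because the only purpose given for these models is the slope, and the same paragraph uses that word for rate of change.

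A reader might infer that the trial will detect a true association about 6% of the time instead of over 90%. The documents do not support that. The 6% is simply the test's false-positive rate, and it applies only if the slope term decides. The 90% needs an assumed effect of about -0.20, assumed variances and six readings per session. Six readings are supported for BAES only; dot probe is a before/after change score, and nothing says APT repeats after each drink.

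It is also fair to say that a between-person correlation is not a false positive under a hypothesis that does not specify within-person association. But the purpose clause asks about within-person change, and Aim 3 opens by distinguishing it from between-person differences. The two should therefore be estimated separately.

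Finally, this is a pilot and these are secondary measures. That limits the consequence but does not remove the mismatch.

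**Conclusion.** The point holds in a limited form. The hypothesis in Sections 4.1 and 8.1 is an association, and the stated purpose of the Aim 3 models is an effect on slope. For BAES, the slope term rejects at about 5% under any constant association, and it can be significant with no average association. The 5% result does not depend on the assumed effect size or variances; it requires only that the main effect is also in the model. The hypothesis goes untested only if inference rests on the slope term.

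How much power the association test would have is not knowable from the documents. The figures of 72–90% at -0.15 and 91–99% at -0.20 are illustrations under two sets of assumed variances for a measure taken at each timepoint. For session- and person-level measures scenario B gives 72% and 40% at -0.20. The plan should be changed, but the defect is one of specification and can be put right before analysis.

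**What to change.** In Section 8.1, replace the purpose clause for these models.

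- **BAES stimulation and sedation:** the test of the hypothesis is the coefficient of the measure's deviation from the participant's own mean. Enter the participant mean as a separate between-person term. Centre timepoint (at 3.5 for timepoints 1–6) and adjust for timepoint, drug and timepoint × drug. State the expected sign for each subscale.
- **APT and dot probe:** test the association as a main effect on satiety, at the level at which each is actually measured. For dot probe that is the before/after change score by session. For APT, state when it is given and use that level.
- **Measure × timepoint:** keep it as a labelled secondary question (does the association change over the session?) that does not decide the association hypothesis.

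The cost is a few sentences of analysis text and one derived variable per measure, with no new data. The downside is that the slope-moderation question becomes secondary.
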